8.5.2.7 Adverse Events/Serious Adverse Events – Definitions

8.5.2.7.1 Adverse Event (AE)

An AE is any untoward medical occurrence in a patient (or a clinical investigation subject), receiving a medicinal product and which does not necessarily have a causal relationship with the treatment. An AE can, therefore, be any unfavourable and unintended sign (including an abnormal clinically significant laboratory finding), symptom, or disease temporally associated with the use of a medicinal (investigational) product, whether or not related to the medicinal (investigational) product.

8.5.2.7.2 Adverse Drug Reaction (ADR)

All untoward and unintended responses to an Investigational Medicinal Product (IMP) related to any dose administered. The definition covers also medication errors and uses outside what is foreseen in the protocol, including misuse and abuse of the product. The definition implies a 'reasonable possibility of a causal relationship between the event and the IMP. This means that there are facts (evidence) or arguments to suggest a causal relationship.

8.5.2.7.3 Intensity (severity) of an Adverse Event / Adverse Drug Reaction

All AEs (including SAEs) are to be accurately recorded on the AE page of the patient's eCRF. Each event will be graded for severity using the classifications of NCI CTCAE* v4.03 (see 14.4). The highest intensity grade reached in a given cycle should be reported in the e-CRF:

- **Mild (Grade 1)** Mild; asymptomatic or mild symptoms; clinical or diagnostic observations only; intervention not indicated.
- **Moderate (Grade 2)** Moderate; minimal, local or noninvasive intervention indicated; limiting age-appropriate instrumental activity of daily living.
- Severe (Grade 3) Severe or medically significant but not immediately life-threatening; hospitalization or prolongation of hospitalization indicated; disabling; limiting self-care activity of daily living.
- Life-threatening (Grade 4) Life-threatening consequences; urgent intervention indicated.
- **Death (Grade 5)** Related to adverse event.

NOTE: In case of an AE/ADR consisting of a laboratory abnormality, its intensity (severity) should be ranged based on the level of abnormality of the out –of-range value and/or its interference on patient ability to perform daily routine activities, as above defined. A severe AE, as defined by the above grading scale, is NOT the same as serious AE which is defined in $\S8.5.2.7.4$.

* Common Terminology Criteria for Adverse Events (CTCAE) Version 4.0. Published: May 28, 2009 (v4.03: June 14, 2010). U.S.DEPARTMENT OF HEALTH AND HUMAN SERVICES National Institutes of Health National Cancer Institute (please refer to Appendix IV).

8.5.2.7.4 Serious Adverse Event (SAE) / Serious Adverse Drug Reaction (SADR)

Any untoward medical occurrence or effect that at any dose:

- results in death.
- is life-threatening.

NOTE: the term life-threatening in the definition of "serious" refers to an event in which the patient was at risk of death at the time of the event; it does not refer to an event which hypothetically might have caused death if it were more severe.

- requires patient hospitalisation or prolongation of existing hospitalisation.
- results in persistent or significant disability/incapacity.
- is a congenital anomaly/birth defect.
- is an 'important medical event' that may jeopardise the patient or may require an intervention to prevent one of the above characteristics/consequences.

NOTE: Hospitalisation lasting less than 24 hours or pre-planned hospitalisation for medical intervention, such as chemotherapy administration, shall not qualify as SAE.

Any other AE/ADR which is not included in the above definitions will be considered as nonserious.

The Investigator should also promptly report all the SAEs to the Sponsor's Drug Safety Manager (DSM, see §8.6).

8.5.2.7.5 Unexpected Adverse Drug Reaction

An ADR, the nature or intensity of which is not consistent with the applicable product 'safety reference information (e.g. IB for an unauthorised investigational product or summary of product characteristics (SmPC) for an authorised product).

Any other ADR which is not included in the above definition will be considered as expected.

NOTE: In this study, the reference document is the MEN1112 IB, last version approved..

8.5.2.7.6 Algorithm for Causality Assessment of Adverse Events

The causality (causal relationship to the study drug) of AEs will be assessed based on the following algorithm:

1. Certainly related: An AE, including a laboratory test abnormality assessed as CS, is considered certainly related to a drug when it occurs in a plausible time relation to the administration of the drug, and which cannot be explained by concurrent disease or other drugs or chemicals. The response to withdrawal of the drug (de-challenge) should be clinically plausible. The event must be definitely related, pharmacologically or phenomenologically, using a satisfactory re-challenge procedure if necessary.

2. Probably related: An AE, including a laboratory test abnormality assessed as CS, is considered probably related to a drug when it occurs in a reasonable time relation to the administration of the drug, is unlikely to be attributed to concurrent disease or other drugs or chemicals, and which follows a clinically reasonable response on withdrawal (de-challenge). Re-challenge information (AE reappearance after drug reintroduction) is not required to fulfil this definition.

3. Possibly related: An AE, including a laboratory test abnormality assessed as CS, is considered possibly related to a drug when it occurs in a reasonable time relation to the administration of the drug, or it could also be explained by concurrent disease or other drugs or chemicals. Information on drug withdrawal (de-challenge) may be lacking or unclear.

4. Unlikely related: An AE, including a laboratory test abnormality assessed as CS, is considered unlikely related to a drug when other drugs, chemicals or underlying disease provide plausible explanations and/or the temporal relation to the administration of the drug makes a causal relation improbable.

5. Not related: An AE, including a laboratory test abnormality assessed as CS, is considered not related to the use of a drug in case of existence of a clear alternative explanation and/or unreasonable temporal relationship, and/or non plausibility.

6. Unassessable/unclassifiable: The relationship between drug and AE, including a laboratory test abnormality assessed as CS, is considered unassessable/unclassifiable when a report, suggesting an AE, cannot be judged because information is insufficient or contradictory and cannot be supplemented or verified.

An AE in which the relationship is ranked 1, 2, 3 or 6 is defined as an ADR. AEs ranked 4 or 5 are not considered as ADRs.

8.5.2.8 Monitoring and Recording of Adverse Events

The Investigator is responsible for the detection and documentation of events meeting the definition of AE, as provided in this protocol (see § 8.5.2.7.1).

All AEs, whether or not thought to be drug related, must be actively followed-up and recorded by the Investigator (or designee) in the source documents and in the appropriate section of the e-CRF throughout the whole study duration, starting from the Informed Consent signature to the End of Study Visit or 70 days after last study drug administration whichever occurs last.

NOTE: An AE will be considered as **'Treatment-Emergent Signs and Symptoms (TESS)'** if it occurs for the first time or if it worsens in terms of seriousness or severity after the first study drug intake (Visit 1).

8.5.3 Pharmacokinetic Evaluation

Blood samples for MEN1112 serum concentration measurements will be taken during Treatment phase and End of Treatment as depicted in § 14.2. If any interruption occurs during Cycle 1 and the 3^{rd} infusion of Cycle 2 (i.e. where the PK is evaluated), blood sampling for PK & exploratory tests will be taken at the time of each infusion interruption and just before each infusion resumption.

$\begin{array}{ll} C_{max} & \mbox{Maximum observed serum concentration.} \\ t_{max} & \mbox{Time to } C_{max}. \\ C_{last} & \mbox{Last quantifiable serum concentration.} \\ t_{last} & \mbox{Time to } C_{last}. \\ C_{trough} & \mbox{Pre-dose serum concentration.} \\ C_{avg} & \mbox{AUC from dose time to } \tau \mbox{ (i.e. dosing interval) divided by } \tau \end{array}$

k _e	Apparent terminal elimination rate constant, estimated by log- linear regression analysis on serum concentrations visually assessed to be on the terminal log-linear phase.
$t_{\frac{1}{2}}$	The terminal serum half-life, calculated according to the following equation: $t_{1/2} = \frac{0.693}{k_e}$
AUC _(0-t)	Area under the serum concentration-time curves from time zero (pre-dose) to the time of the last quantifiable concentration, calculated by means of the linear-log trapezoidal method.
$\mathrm{AUC}_{(0-\infty)}$	Area under the serum concentration-time curve from time zero to infinity, calculated according to the following equation: $AUC = AUC + \frac{C_{last}}{C_{last}}$
	$moc_{(0-\infty)} = moc_{(0-t)} + k_e$
%AUC _{ex}	The percentage of AUC _(0-∞) obtained by extrapolation calculated as follows: $AUC_{ex}(\%) = \frac{AUC_{(0-∞)} - AUC_{(0-t)}}{AUC_{(0-∞)}} \cdot 100$
CL	Systemic clearance, calculated according to the following equation: $CL = \frac{Dose}{AUC_{(0-\infty)}}$
V _{ss}	Volume of distribution at steady state, calculated according to the following equation: $V_{ss} = CL \cdot MRT$
V _d	Volume of distribution based on the terminal phase, calculated according to the following equation:
	$V_d = \frac{Dose}{k_e \cdot AUC_{(0-\infty)}}$
$AUMC_{(0-\infty)}$	The area under the first moment curve from zero to infinity calculated using the equation:
	$AUMC_{(0-\infty)} = \sum_{i=0}^{n-1} \frac{t_{i+1} - t_i}{2} (C_i t_i + C_{i+1} t_{i+1}) + \frac{tlast \cdot Clast}{k_e} + \frac{Clast}{k_e^2}$
	$+\frac{t \cdot C_t}{\lambda_z} + \frac{C_t}{\lambda_z^2} + \frac{t \cdot C_t}{\lambda_z} + \frac{C_t}{\lambda_z^2} + \frac{t \cdot C_t}{\lambda_z^2} + \frac{C_t}{\lambda_z^2}$
MRT	Mean residence time (for drug given with a constant infusion rate over
	a period T _{inf}) was calculated as: $MRT = \frac{AUMC_{(0-\infty)}}{AUC_{(0-\infty)}} - \frac{T_{inf}}{2}$
Ro	Accumulation ratio calculated as: $Ro = \frac{1}{ 1 - e^{-k_c \tau} }$

PK parameters will be calculated, as data permit, following each of the three doses of the first *"ramp-up"* administration visit during Cycle 1 and following the third *"one-shot"* administration visit during Cycle 2.

The following PK variables will be assessed following the 1^{st} and 2^{nd} dose of the first *"ramp-up"* administration visit during Cycle 1:

• C_{max}, t_{max}, C_{trough}, C_{avg}, AUC_(0-t)

The following PK variables will be assessed following the 3^{rd} dose of the first "*ramp-up*" administration visit during Cycle 1:

C_{max}, t_{max}, C_{trough}, C_{avg}, C_{last}, t_{last}, AUC_(0-t), AUC_(0-∞), %AUC_{ex}, k_e, t_{1/2}, CL, V_{ss}, Vd, AUMC_(0-∞), MRT.

Total AUC following the first *"ramp-up"* administration visit during Cycle 1 will be calculated as the sum of $AUC_{(0-t)}$ related to each dose.

The following pharmacokinetic variables will be assessed following the 3rd "*one-shot*" administration visit during Cycle 2:

C_{max}, t_{max}, C_{trough}, C_{avg}, C_{last}, t_{last}, AUC_(0-t), AUC_(0-∞), %AUC_{ex}, k_e, t_{1/2}, CL, V_{ss}, Vd, AUMC_(0-∞), MRT, accumulation ratio (Ro).

Actual PK sampling times will be used in the derivation of PK parameters. Alternatively, it is also acceptable to consider the planned sampling times if they do not deviate by more than 5% from the actual. Planned sampling times may be used as a replacement for unknown or missing actual times. The calculation of the parameters listed above and others will depend upon the results of the drug concentration assay and the duration of drug infusions.

For the calculation of individual pharmacokinetic parameters, values Below the Lower Limit Of Quantification (BLLOQ) will be handled as follows:

- 1. BLLOQ values located before the t_{max} of their affiliating curve will be transformed to zero.
- If a BLLOQ value located after the t_{max} falls between two quantifiable concentrations, it will be omitted from the pharmacokinetic analysis.
- 3. If, within a dosing interval, two or more BLLOQ values occur in succession after quantifiable concentrations, the profile will be deemed to have terminated at the first BLLOQ value and any subsequent concentrations in that dosing interval will be omitted from the non-compartmental analysis.
- 4. In some circumstances, when a pharmacokinetic rationale exists, BLLOQ values may be set to some other values, e.g., half of the Lower Limit of Quantification (LLOQ).

Concentrations reported as >LLOQ at time zero, when the subject has not previously been dosed, will be set to zero.

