	any time point between CR, CRi and partial remission ([PR]:
	all haematological criteria for CR with bone marrow blasts 5-
	25% and decrease of pre-treatment bone marrow blast
	percentage by at least 50%).
•	Duration of CRc: number of days between the date of CR/CRi
	achievement and the date of the last assessment confirming
	CR/CRi.
•	Overall Survival (OS), defined as the number of days between
	the first study drug administration and death from any cause.
-	Correlation of baseline characteristics with clinical activity of
	MEN1112.

Immunogenicity	Incidence of anti-MEN1112 auto-antibodies.
Endpoint Pharmacokinatic	
endpoints	PK parameters will be calculated, as data permit, following each of
	the three doses of the first "ramp-up" administration visit during
	Cycle 1 and following the third "one-shot" administration visit
	during Cycle 2.
	The following PK variables will be assessed following the 1 st and 2 nd
	dose of the first "ramp-up" administration visit during Cycle 1:
	C _{max} , t _{max} , C _{trough} , C _{avg} , AUC _(0-t)
	The following PK variables will be assessed following the 3 rd dose of
	the first "ramp-up" administration visit during Cycle 1:
	C _{max} , t _{max} , C _{trough} , C _{avg} , C _{last} , t _{last} , AUC _(0-t) , AUC _(0-∞) , %AUC _{ex} , k _e , t _{1/2} ,
	CL, V _{ss} , Vd, AUMC _(0-∞) , MRT.
	Total AUC following the first "ramp-up" administration visit during
	Cycle 1 will be calculated as the sum of $AUC_{(0-t)}$ related to each dose.
	The following pharmacokinetic variables will be assessed following
	the 3 rd "one-shot" administration visit during Cycle 2:
	Cmax, tmax, Ctrough, Cavg, Clast, tlast, AUC(0-t), AUC(0-co), %AUCex, ke, t1/2,
	CL, V _{ss} , Vd, AUMC _(0-∞) , MRT, accumulation ratio (Ro).
Safety endpoints	 Incidence, severity, seriousness and treatment related
	causality of Treatment Emergent Signs and Symptoms
	(TESSs).
	 Frequency of clinically significant abnormalities in physical
	examination, safety laboratory tests, vital signs and 12-Lead
	ECG.
Sample size	Due to the nature of the study, no formal sample size calculation is
-	applicable.
	Starting from protocol version 6.1/6.2 up to approximately 6 DLT
	evaluable patients per dose level will be treated with MFN1112
	during the dose escalation phase while up to approximately 30
	patients will be treated in the cohort expansion phase. Considering

that the patients no-DLT evaluable during the dose escalation phase

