6.2.4.3 Overview of clinical pharmacokinetics

MEN1112 serum concentrations from Cohort 0.1 mg/kg to Cohort 1.7 mg/kg of ARMY-1 study were measured and an interim PK analysis was performed for 38 subjects after a single IV infusion and for 8 subjects after six consecutive IV infusions. The pharmacokinetics of MEN1112 in human were characterised by a dose-dependent behaviour after both single and repeat dose administration, as shown by a more than proportional increase in AUC_{0-inf} in the dose-range 0.1-2.5 mg/kg. MEN1112 was slowly cleared from the body, with a mean half-life ranging from 10.8 to 41.8 hr and from 12.8 to 146.4 hr after single and repeat dose, respectively. The values obtained for volume of distribution at steady state were similar to total blood volume (i.e. 5 L). Estimates of clearance were also low (0.02 - 0.9 L/hr) and in the range of those reported for other monoclonal antibodies. The magnitude of inter-individual variability in MEN1112 disposition is large in the explored dose-range of 0.1-2.5 mg/kg.

6.3 **RISK BENEFIT ASSESSMENT**

The medical need for AML and MDS is yet highly unmet and new treatments are urgently needed for either disease.

MEN1112 is a defucosylated Monoclonal Antibody with high affinity binding to Bst1/CD157 antigen, which is expressed at high prevalence on both AML and MDS cells.

Due to its ability to deplete AML and MDS blasts, even in the presence of low NK cells percentage, MEN1112 is considered to have the potential to represent a new targeted therapeutic opportunity in both AML and MDS patients. the single agent activity of MEN1112 is under clinical investigation in patients with relapsed or refractory AML in the ARMY-1 trial. In this trial, the MTD of the "*one-shot*" administration schedule has been identified at 1.7 mg/kg following the occurrence of two DLT events in two patients treated at 2.5 mg/kg dose level

. The Sponsor therefore performed an in-depth review of the safety

profile of MEN1112, with a particular focus on the four patients

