A mechanistic Target-Mediated Drug Disposition (TMDD) population PK model has been developed from free circulating MEN1112 concentration from ARMY-1 study (MEN1112-PK-01). The TMDD model was used in simulation to explore different *"ramp-up"* dosing schedule scenarios. Upon the aforementioned PK modelling simulations, a 3-day *"ramp-up"* approach was chosen. The *"ramp-up"* dosing escalation and the whole treatment plan will thus be as following:

DOSE LEVEL	CYCLE 1	CYCLE 2
1.7 mg/kg	Visit 1/Day 1: 0.1 mg/kg	Visit 16/Day 22: 1.7 mg/kg
	Visit 2/Day 2: 0.6 mg/kg	Visit 20/Day 29: 1.7 mg/kg
	Visit 3/Day 3: 1.0 mg/kg	Visit 24/Day 36: 1.7 mg/kg
	Visit 8/Day 8: 0.1 mg/kg	
	Visit 9/Day 9: 0.6 mg/kg	
	Visit 10/Day 10: 1.0 mg/kg	
	Visit 12/Day 15: 1.7 mg/kg	
2.0 mg/kg	Visit 1/Day 1: 0.1 mg/kg	Visit 16/Day 22: 2.0 mg/kg
	Visit 2/Day 2: 0.7 mg/kg	Visit 20/Day 29: 2.0 mg/kg
	Visit 3/Day 3: 1.2 mg/kg	Visit 24/Day 36: 2.0 mg/kg
	Visit 8/Day 8: 0.1 mg/kg	
	Visit 9/Day 9: 0.7 mg/kg	
	Visit 10/Day 10: 1.2 mg/kg	
	Visit 12/Day 15: 2.0 mg/kg	
3.0 mg/kg	Visit 1/Day 1: 0.2 mg/kg	Visit 16/Day 22: 3.0 mg/kg
3.0 mg/kg	Visit 1/Day 1: 0.2 mg/kg Visit 2/Day 2: 1.0 mg/kg	Visit 16/Day 22: 3.0 mg/kg Visit 20/Day 29: 3.0 mg/kg
3.0 mg/kg	Visit 1/Day 1: 0.2 mg/kg Visit 2/Day 2: 1.0 mg/kg Visit 3/Day 3: 1.8 mg/kg	Visit 16/Day 22: 3.0 mg/kg Visit 20/Day 29: 3.0 mg/kg Visit 24/Day 36: 3.0 mg/kg
3.0 mg/kg	Visit 1/Day 1: 0.2 mg/kg Visit 2/Day 2: 1.0 mg/kg Visit 3/Day 3: 1.8 mg/kg Visit 8/Day 8: 0.2 mg/kg	Visit 16/Day 22: 3.0 mg/kg Visit 20/Day 29: 3.0 mg/kg Visit 24/Day 36: 3.0 mg/kg
3.0 mg/kg	Visit 1/Day 1: 0.2 mg/kg Visit 2/Day 2: 1.0 mg/kg Visit 3/Day 3: 1.8 mg/kg Visit 8/Day 8: 0.2 mg/kg Visit 9/Day 9: 1.0 mg/kg	Visit 16/Day 22: 3.0 mg/kg Visit 20/Day 29: 3.0 mg/kg Visit 24/Day 36: 3.0 mg/kg
3.0 mg/kg	Visit 1/Day 1: 0.2 mg/kg Visit 2/Day 2: 1.0 mg/kg Visit 3/Day 3: 1.8 mg/kg Visit 8/Day 8: 0.2 mg/kg Visit 9/Day 9: 1.0 mg/kg Visit 10/Day 10: 1.8 mg/kg	Visit 16/Day 22: 3.0 mg/kg Visit 20/Day 29: 3.0 mg/kg Visit 24/Day 36: 3.0 mg/kg
3.0 mg/kg	Visit 1/Day 1: 0.2 mg/kg Visit 2/Day 2: 1.0 mg/kg Visit 3/Day 3: 1.8 mg/kg Visit 8/Day 8: 0.2 mg/kg Visit 9/Day 9: 1.0 mg/kg Visit 10/Day 10: 1.8 mg/kg Visit 12/Day 15: 3.0 mg/kg	Visit 16/Day 22: 3.0 mg/kg Visit 20/Day 29: 3.0 mg/kg Visit 24/Day 36: 3.0 mg/kg

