7.2 SECONDARY OBJECTIVES

The following will be assessed/determined:

- Safety and tolerability of MEN1112.
- Pharmacokinetic profile after single and repeat doses of MEN1112 following IV

Page 69 of 132

administration.

- Potential of MEN1112 immunogenicity.
- Clinical activity of MEN1112.
- Correlation of baseline patient's and disease characteristics with clinical activity of MEN1112

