8.4.3.1 Dose-level escalation assessment

In place of the Cohort Review Committee (CRC), which was appointed to guide dose escalation decisions up to Protocol Version 4.1, starting from Protocol Version 6.1/6.2, the decision as to whether, or how, to proceed through the dose levels during Step 1 are guided by the iDMSB which will be comprised of independent AML experts.

The iDSMB will meet by telephone to review the latest safety, PK and Pharmacodynamics (PD) (if any) data prior to dose-escalation to a subsequent cohort, and at any time if needed. Appropriate representatives of the Sponsor and the coordinating CRO will also attend and minute the meeting. Decisions of the iDMSB will be documented and sent to the sites.

The iDSMB is empowered to:

• Review the safety data from the first cycle of each cohort during the dose escalation phase of the study and make dose-escalation (or de-escalation) decisions according to the protocol or making adjustments, as needed. AEs occurring in Cycle 2 which meet the definition of a DLT or are considered clinically significant may also be considered in making dose escalation decisions.

- Consider other AEs, or possible trends in AEs, during the dose escalation phase which may provide relevant information for the dose escalation.
- Confirm the MTD or the maximum dose judged to be tolerable for evaluation in Step 2.
- Review safety data for additional patients recruited at the MTD or the maximum dose judged to be tolerable (at least every 2 months).
- Recommend future dose level and dose schedule administration during the study conduct; advise on premedication, concomitant medication and on any individual patient dose adjustments.

Roles and responsibilities of iDSMB as well as meeting schedule and format of information will be set forth in a separate iDSMB Charter prior to start administrating the drug to the first patient under protocol version 6.1/6.2.

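### Under the ramp-up schedule, CL and Vd are calculated only on profiles that still hold drug from earlier doses, with no rule for the residual and no definition of Dose

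*Combined protocol and SAP*

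**What the plan says.** The protocol, section 8.5.3, defines "Systemic clearance, calculated according to the following equation" as Dose/AUC(0-∞), and terminal-phase Vd as Dose/(ke × AUC(0-∞)). Vss is CL × MRT. AUC is counted from the pre-dose sample. Dose is not defined further.

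The synopsis and sections 8.5.3 and 8.5.4.5 state which profiles are analysed: "PK parameters will be calculated, as data permit, following each of" the three doses of the first ramp-up, and after the third Cycle 2 infusion (Day 36). Ramp-up doses 1 and 2 get Cmax, tmax, Ctrough, Cavg and AUC(0-t) only. CL, Vd and Vss are reserved for ramp-up dose 3 and Day 36.

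The rules in section 8.5.3 set a measurable time-zero concentration to zero only in a subject who has never been dosed. A total ramp-up AUC is planned as the sum of the three AUC(0-t) values, but it has no extrapolated tail and is not tied to CL. An accumulation ratio is planned for Day 36 and is not applied to CL or Vd.

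Section 6.2.4.3 describes the earlier one-shot data, "with a mean half-life ranging from 10.8 to 41.8 hr and from 12.8 to 146.4 hr after single and repeat dose, respectively", the repeat-dose figures being "for 8 subjects after six consecutive IV infusions". It also reports dose-dependent kinetics, "as shown by a more than proportional increase in" AUC. Section 6.3 adds: "A mechanistic Target-Mediated Drug Disposition (TMDD) population PK model has been developed".

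**The concern.** Dose/AUC(0-∞) is a clearance only if all the drug in the AUC came from that dose. Ramp-up dose 3 follows infusions on the two preceding days. Day 36 follows five earlier administration visits (nine infusions). From the pre-dose sample onward the body eliminates Dose plus residual, while the numerator counts Dose alone. Average clearance over that window is (Dose + residual)/AUC, so the planned figure falls short by the factor Dose/(Dose + residual), and Vd falls by the same factor. This is mass balance and does not require linear kinetics.

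One secondary objective in section 7.2 is the "Pharmacokinetic profile after single and repeat doses of MEN1112 following IV" administration. Section 9.3.3 plans descriptive PK summaries, so CL and Vd would be reported as they stand. Because the bias differs between the two profiles, a Cycle 1 versus Cycle 2 comparison could show a change in clearance that is only carry-over.

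**Working it through.** The plan states no expected CL or carry-over, so there is no figure to reproduce.

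**Inputs.** Doses are from the section 8.4.5 table; infusions last 6 h at constant rate (section 8.5.1); half-lives are from section 6.2.4.3. Ramp-up spacing, start to start, is taken as 24 h, or as 30 h if the day that separates Visits 1, 2 and 3 runs from the end of each infusion (assumption). The model is linear, one-compartment (assumption, for illustration).

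**Formulas.** With k = ln 2/half-life, the fraction of a dose left s hours after its infusion began is f(s) = [(e^(6k) − 1)/(6k)] × e^(−ks). Planned/true CL = planned/true Vd = Dose/(Dose + residual).

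**Worked case** (1.7 mg/kg level, 24 h spacing):
- Half-life 10.8 h: f(24) = 0.261, f(48) = 0.056. Residual = 0.6 × 0.261 + 0.1 × 0.056 = 0.162 mg/kg. Ratio = 1.0/1.162 = 0.860.
- Half-life 41.8 h: f(24) = 0.706, f(48) = 0.474. Residual = 0.424 + 0.047 = 0.471 mg/kg. Ratio = 1.0/1.471 = 0.680.

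**Ramp-up dose 3, planned/true CL and Vd:**

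| Level (doses 1/2/3, mg/kg) | 24 h spacing, 10.8 h | 24 h, 41.8 h | 30 h, 10.8 h | 30 h, 41.8 h |
|---|---|---|---|---|
| 1.7 (0.1/0.6/1.0) | 0.860 | 0.680 | 0.901 | 0.703 |
| 2.0 (0.1/0.7/1.2) | 0.864 | 0.689 | 0.904 | 0.712 |
| 3.0 (0.2/1.0/1.8) | 0.868 | 0.692 | 0.908 | 0.715 |
| 5.0 (0.3/1.7/3.0) | 0.867 | 0.691 | 0.906 | 0.714 |

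The shortfall is 13–14% to 31–32% at 24 h spacing and 9–10% to 28–30% at 30 h. Non-compartmental analysis simulated at the Appendix II times agrees within 0.01; without the earlier doses it returns 1.00–1.01, so sampling error is not the cause.

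**Day 36** (same at all levels): residual/Dose is 0.0001, 0.069 and 0.831 at 12.8, 41.8 and 146.4 h, giving ratios 1.000, 0.935 and 0.546. At assumed intermediate half-lives of 72 and 100 h they are 0.796 and 0.682.

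**Other reading of Dose.** Total ramp-up dose over the dose-3 AUC gives, in the second worked case, 1.7/1.471 = 1.156. Across levels, spacings and half-lives, CL is 15–53% too high.

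**Non-linear check** (assumed linear plus saturable elimination, 180 parameter sets): planned CL was 0.563–1.000 of the CL of dose 3 given alone, never above it.

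**Vss** (assumed linear two-compartment kinetics, 18 sets): planned CL was 0.676–0.891 of true, but Vss was 0.707–1.123, so its direction is not settled.

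**The case against.** Several counter-arguments carry weight.

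*Dose is undefined.* Section 8.4.5 describes one complete dose split over three days, so for the ramp-up a reader could take Dose as the total. That stands: the text does not establish a downward bias on every reading. But the total-dose reading is also wrong, in the other direction.

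*Carry-over-free data exist.* A reader might infer that the study yields no clean CL at all. It does: section 6.2.4.3 reports 38 subjects after a single one-shot infusion. The point is confined to the ramp-up schedule.

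*The sizes depend on the model.* The kinetics are non-linear, half-lives are not mapped to doses, and 146.4 h is the top of a range of means from 8 subjects. The percentages are illustrations, not bounds, and 45% is not a typical Day 36 bias.

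*Part of the Day 36 remedy is already planned.* Cavg × τ is AUC(0-τ), so a reader could recover the corrected value. True, but the plan does not connect it to CL.

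*Dose/AUC(0-τ) holds only near steady state.* This stands. Suppose the half-life jumps at Day 36 (an extreme assumption). From 41.8 to 146.4 h, Dose/AUC(0-τ) is 1.72 of true CL, against 0.94 as planned. From 72 to 146.4 h they are 1.47 and 0.80. The fix therefore needs a condition.

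*The SAP can settle it.* Section 9.3.3 leaves additional analyses to the SAP, but the CL formula is already fixed in section 8.5.3.

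**Conclusion.** The formulas for CL and Vd do not fit the two profiles to which the current schedule applies them. With Dose as the dose that starts the profile, both are low whenever residual drug is present. Under the illustrative model that means about 9–32% after ramp-up dose 3, across the whole reported range of mean single-dose half-lives. On Day 36 it means 0–6.5% at 12.8–41.8 h and more only at longer half-lives. The direction rests on mass balance and that reading of Dose; the sizes rest on linear one-compartment kinetics and half-lives from the one-shot schedule.

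A reader might infer that dose escalation is compromised. The documents do not support that. The DLT and MTD definitions use no PK parameter. The iDSMB will "review the latest safety, PK and Pharmacodynamics (PD) (if any) data prior to dose-escalation to a subsequent cohort" (section 8.4.3.1), but the protocol does not say that CL is among those data. The correction should be made because it protects a secondary objective at little cost.

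**What to change.** Define Dose and AUC for each profile in section 8.5.3 or the SAP.

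1. **Ramp-up.** CL = (dose 1 + dose 2 + dose 3)/[AUC from dose 1 to the pre-dose 2 sample + AUC from dose 2 to the pre-dose 3 sample + AUC(0-∞) after dose 3], labelled as average apparent CL over the ramp-up. On the scheduled samples this gave 1.010 (10.8 h) and 1.001 (41.8 h) of true CL; without the tail it gave 1.34–1.36 at 41.8 h. Where the pre-dose 3 concentration is below LLOQ, or below a small share of Cmax fixed in the SAP, also report dose 3/AUC(0-∞) as the estimate for dose 3 itself. In the saturable check, when pre-dose 3 was at or below 5% of Cmax (87 of 180 sets), that formula gave 0.938–1.000 of the CL of dose 3 alone and the total-dose formula 1.084–1.529.
2. **Day 36.** CL = Dose/AUC(0-τ), τ = 168 h from the start of infusion, equivalently Dose/(Cavg × τ). Interpolate between the 144 h and one-week post-infusion samples. Under constant linear kinetics this gave 1.008, 1.001 and 1.002 of true CL at 12.8, 41.8 and 146.4 h. Report it as CL only if the pre-dose and 168 h concentrations agree within a margin fixed in the SAP; otherwise label it apparent and not at steady state. In the 41.8 to 146.4 h example the amounts are 0.069 and 0.489 of the dose, so the check would catch it.
3. **Vd** = corrected CL/ke.
4. **Vss.** Keep it, flagged as affected by carry-over in an uncertain direction.
5. **Interpretation.** Do not read a Cycle 1 versus Cycle 2 difference in uncorrected CL as a change in clearance.

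The cost is wording and a little extra PK analysis, with no new samples. The drawback is that under non-linear kinetics the ramp-up CL is a three-dose average, not the CL of dose 3.
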